8.2.5. Analysis of the secondary end points

8.2.5.1. Sunitinib treatment

Populations analyzed: Safety population

End points:

The analysis of sunitinib treatment methods will be carried out using the following indicators:

▪ **Description of dose reductions**

- Proportion of patients with at least one dose reduction during the period of sunitinib treatment;
- Reasons for the dose reduction: Proportion of patients involved on at least one occasion for each of the reasons for a dose reduction;
- Average dose reduction.

▪ **Description of interruptions to treatment**

- Proportion of patients who interrupted sunitinib treatment temporarily during treatment (including declared temporary interruptions and cases in which the start of the later cycle was deferred);
- Mean duration (in days) of interruptions to treatment by patient (declared duration of interruption or number of days delay identified for the start of the subsequent cycle);
- Reason for interruptions: Proportion of patients involved on at least one occasion for each of the reasons for interruption of treatment (AE, radiotherapy, surgery or other).

▪ **Description of permanent treatment discontinuations**

- Proportion of patients who discontinued sunitinib permanently;
- Reason for discontinuation: proportion of patients involved on at least one occasion for each of the reasons for discontinuation;
- Duration of treatment with sunitinib: time between starting sunitinib and the notified date to discontinue it or the date of the last consultation if sunitinib treatment was not stopped;
- Number of treatment cycles before discontinuation.

The analysis will be performed both on an overall basis and according to the number of calls made by the call center.

8.2.5.2. Number of unplanned medical procedures, whether or not related to Sunitinib

Analysis population: Safety population

Analysis:

The purpose of estimating the number of unplanned medical procedures particularly involves those unplanned consultations and hospitalizations, whether or not related to sunitinib and declared at each follow-up visit.

At each theoretical follow-up time (end of cycles 1, 2 and 4 and overall), the following indicators will be described on an overall basis:

- Proportion with at least 1 consultation, at least 1 hospitalization, resulting in at least 1 planned or unplanned call to a health professional;
- Average number of consultations and hospitalizations (two different indicators) both planned and unplanned and the total number per cycle per patient;
- Total number of consultations and hospitalizations (single indicator) by cycle during sunitinib treatment. The number of planned, unplanned and the total number of calls to a health professional by cycle, by patient will also be described for descriptive purposes.

The analysis will be performed on an overall basis and by the number of calls made by the call center.

8.2.5.3. Adherence to treatment

Population analyzed: Safety population

Analysis:

Adherence to sunitinib treatment will be assessed from the standardized, validated, Morisky self-completed questionnaire (MMAS-4: 4-item Morisky Medication Adherence Scale), completed by the patients at the 6 wee follow-up visit in cycles 1, 2 and 4. This questionnaire consists of 4 items each with two response options “Yes” and “No”.

An **MMAS-4 score** will be calculated as the number of “Yes” responses and will be between 0 and 4, a low score representing improved adherence. The score will be missing if one of the items has not been completed.

A classification using the MMAS-4 score will be used to categorize adherence into levels [3; 4]:

- High adherence: score of 0;
- Average adherence: score of 1 or 2;
- Poor adherence: score of 3 or 4.

At each measurement time (end of cycles 1, 2 and 4), the following indicators will be described:

- **average adherence score;**
- **proportion of patients by a patient adherence level;**
- **the proportion of “adherent” patients**, defined as patients with an MMAS score of 0 and the proportion of “non-adherent” patients as patients with a score of at least 1 [6].
- **An assessment of patient behavior in terms of their treatment when they develop an AE (binary indicator (Yes/No) for reduction or adjustment of treatment).**

In order to examine the change in adherence by patient, the mean difference in patient score between the assessment at the end of cycle 1 and the assessment at cycle 4 will be described.

The analysis will be performed on an overall basis and by the number of calls made by the call center.

In addition and only for informative purposes, the Morisky questionnaire will also be completed through the call center during the call on W4 of cycles 1, 2 and 4 and in the “Call Center” group. This assessment will be used:

- firstly to measure adherence at the end of the 4th week of treatment (immediately before the treatment break) from the derived criteria described above (average score, proportion of adherent patients);
- secondly, to estimate (subject to sufficient numbers being available) good consistency between patient declarations between the measurement on W4 and the consultation on W6 during which the patient will complete his/her self-administered questionnaire.

Concordance will only be measured for informative purposes as the questionnaire has been validated for self-completion by the patient him/herself and not as one administered by a third party (potential declaration bias concerning the issue of adherence).

The MMAS-4 score ranges from 0 to 4 (discrete quantitative variable), and can be considered to be qualitative index. Consistency between adherence at week 4 assessed by telephone and adherence at week 6 assessed in writing will be considered using the Kappa coefficient.

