7. MANAGEMENT OF MISSING VALUES

The data from patients were recorded on an eCRF, except for the paper self-completed adherence and patient satisfaction questionnaires. Mandatory fields and consistency controls will be used to check data registered at the time. This strategy will be used to reduce missing data points or inconsistencies, particularly those concerning the major end points (AE, grades of AE and response to treatment etc.).

The analyses will be performed on the available data (“observed case analysis”), using the assumption that missing data are non-informative. The numbers of missing data points will be presented for each variable.

The response analysis will also be conducted on the FAS population by imputing missing responses as failure (= progression).

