9.5.3. Adherence to treatment

Table 39: Morisky scale items during the follow-up period (safety population)

		End of cycle 1 (N=xxx)	End of cycle 2 (N=xxx)	End of cycle 4 (N=xxx)
Morisky questionnaire items				
Has already forgotten to take treatment	Yes	xx (xx%)	xx (xx%)	xx (xx%)
	No	xx (xx%)	xx (xx%)	xx (xx%)
Occasionally has difficulty remembering to take treatment	Yes	xx (xx%)	xx (xx%)	xx (xx%)
	No	xx (xx%)	xx (xx%)	xx (xx%)
Occasionally stops taking treatment when he/she feels better	Yes	xx (xx%)	xx (xx%)	xx (xx%)
	No	xx (xx%)	xx (xx%)	xx (xx%)
Occasionally stops taking treatment when he/she feels less well	Yes	xx (xx%)	xx (xx%)	xx (xx%)
	No	xx (xx%)	xx (xx%)	xx (xx%)
Additional question about the AEs				
Occasionally reduced or adjusts treatment when an adverse event develops	Yes	xx (xx%)	xx (xx%)	xx (xx%)
	No	xx (xx%)	xx (xx%)	xx (xx%)

Table 40: Assessment of adherence during the follow-up period (safety population)

		End of cycle 1 (N=xxx)	End of cycle 2 (N=xxx)	End of cycle 4 (N=xxx)
MMAS-4 score (adherence score)*				
Number analyzed		xxx	xxx	xxx
Mean (\pm SD)	xx (\pm xx)	xx (\pm xx)	xx (\pm xx)	xx (\pm xx)
Median	xx	xx	xx	xx
Min-Max	xx - xx	xx - xx	xx - xx	xx - xx
Level of adherence				
High: 0		xx (xx%)	xx (xx%)	xx (xx%)
Mean: 1 or 2		xx (xx%)	xx (xx%)	xx (xx%)
Low: 3 or 4		xx (xx%)	xx (xx%)	xx (xx%)
Missing value		xx -	xx -	xx -
“Adherent” patient				
Yes: 0		xx (xx%)	xx (xx%)	xx (xx%)
No: ≥ 1		xx (xx%)	xx (xx%)	xx (xx%)
Missing value		xx -	xx -	xx -
Difference in adherence score between the end of C1 and C4				
Number analyzed		-	-	xxx
Mean (\pm SD)		-	-	xx (\pm xx)
Median		-	-	xx
Min-Max		-	-	xx - xx
Difference in adherence score between the end of C1 and C4				
Improvement		-	-	xx (xx%)
Stable score		-	-	xx (xx%)
Deterioration		-	-	xx (xx%)
Missing value		-	-	xx -

* From 0 to 4: a low score represents improved adherence.

- **Assessment of adherence in week 4 of cycles 1, 2 and 4 by telephone in patients in the CC arm**

Table 41: Morisky scale items in week 4 of cycles 1, 2 and 4 (safety population)

Carried out by telephone		Call, W4 cycle 1 (N=xxx)	Call, W4 cycle 2 (N=xxx)	Call, W4 cycle 4 (N=xxx)
Morisky questionnaire items:				
Has already forgotten to take treatment	Yes	xx (xx%)	xx (xx%)	xx (xx%)
	No	xx (xx%)	xx (xx%)	xx (xx%)
Occasionally has difficulty remembering to take treatment	Yes	xx (xx%)	xx (xx%)	xx (xx%)
	No	xx (xx%)	xx (xx%)	xx (xx%)

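### The blank-item rule for the Morisky score drops forms that the SAP's own cut already classes as non-adherent, so the adherent proportion can exceed what the returned forms allow

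*SAP*

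**What the plan says.** The proportion of adherent patients is a named secondary end point (SAP 6.2). SAP 8.2.5.3 builds it in three steps:

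- **Score.** The MMAS-4 score "will be calculated as the number of “Yes” responses and will be between 0 and 4, a low score representing improved adherence".
- **Binary cut.** Adherent patients are "patients with an MMAS score of 0 and the proportion of “non-adherent” patients as patients with a score of at least 1".
- **Blank items.** "The score will be missing if one of the items has not been completed".

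SAP section 7 sets the general rule: "The analyses will be performed on the available data (“observed case analysis”), using the assumption that missing data are non-informative". The only alternative handling of missing data there is for tumour response: "The response analysis will also be conducted on the FAS population by imputing missing responses as failure (= progression". Adherence has no sensitivity analysis. The same section says that the adherence form is on paper, outside the eCRF with its mandatory fields, so blanks can occur.

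In the shell of Table 40 (SAP 9.5.3), the Yes and No rows of the adherent indicator carry a count and a percentage. The missing row carries a count and a dash, so missing scores lie outside the percentage base. Table 42 (telephone, week 4) and Table 62 (standard follow-up) have the same layout.

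Protocol 7.3.2 scores the scale in the opposite direction and has no blank-item rule. That does not affect this point.

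**The concern.** Under the SAP's cut, one 'Yes' settles the class: the score is at least 1 whatever the blank would have been. The blank-item rule still sets such a form to missing, and it leaves the binary indicator.

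The loss is one-sided. Being adherent takes four 'No' answers, so an incomplete form can show that a patient is non-adherent but never that a patient is adherent. Every discarded form whose class is known is therefore a non-adherent one. At stake is whether the printed proportion is a value that the study's own returned forms could produce.

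**Working it through.** The plan states no adherence figure, so there is none to reproduce. The score, cut, blank-item rule and percentage base come from SAP 8.2.5.3, section 7 and Table 40. All counts below are assumptions.

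**1. How often a blank leaves the class open.** Four items, each 'Yes', 'No' or blank, give 3^4 = 81 patterns. Of these, 2^4 = 16 are complete and 65 have a blank. Of the 65, 15 contain no 'Yes' (14 with at least one 'No', 1 wholly blank) and 50 contain a 'Yes'. Those 50 are certainly non-adherent, yet the rule makes them missing. These are pattern counts, not frequencies.

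**2. Formulas.** Among returned forms let C = complete, A = complete with score 0, K = incomplete with at least one 'Yes', U = incomplete with no 'Yes'.

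- SAP figure: A/C
- Lowest value the forms allow (every U non-adherent): A/(C+K+U)
- Highest value (every U adherent): (A+U)/(C+K+U)

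**3. When the SAP figure exceeds the highest value.** A/C > (A+U)/(C+K+U) means A(C+K+U) > C(A+U), hence A(K+U) > CU, hence **K/(K+U) > 1 − A/C**. In words: incomplete forms show a 'Yes' more often than complete forms do. A/C never falls below the lowest value.

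**4. Illustrations (assumed counts).**

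| C | A | K | U | SAP A/C | Lowest | Highest | SAP minus highest |
|---|---|---|---|---|---|---|---|
| 72 | 54 | 5 | 3 | 75.0% | 54/80 = 67.5% | 57/80 = 71.3% | 3.75 points above |
| 76 | 57 | 2 | 2 | 75.0% | 57/80 = 71.3% | 59/80 = 73.8% | 1.25 above |
| 68 | 51 | 6 | 6 | 75.0% | 51/80 = 63.8% | 57/80 = 71.3% | 3.75 above |
| 80 | 60 | 20 | 0 | 75.0% | 60/100 = 60.0% | 60.0% | 15 above |
| 72 | 36 | 4 | 4 | 50.0% | 36/80 = 45.0% | 40/80 = 50.0% | none |
| 90 | 60 | 3 | 7 | 66.7% | 60/100 = 60.0% | 67/100 = 67.0% | inside the range |

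In the first row, 5/8 = 0.625 exceeds 1 − 0.75 = 0.25. In the fifth, 4/8 = 0.50 equals 1 − 0.50, so there is no excess.

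**5. Blanks unrelated to the answers.** Assume that 60% are truly adherent; that the non-adherent have one, two, three or four 'Yes' in proportions 60/25/10/5%; that each item is blank independently with probability q; and that wholly blank forms are set aside.

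| q | SAP figure | Limits | 'Yes' forms restored, U still dropped |
|---|---|---|---|
| 2% | 60.0% | 55.3% to 60.5% | 58.3% |
| 5% | 60.0% | 48.9% to 61.2% | 55.8% |
| 10% | 60.0% | 39.4% to 62.5% | 51.2% |

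Here the SAP figure is right and lies within the limits. Restoring only the known 'Yes' forms biases it downwards.

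**6. What the tables reveal.** Total 'Yes' answers to the four items in Table 39, minus the mean score times the number analysed in Table 40, gives the number Y of 'Yes' answers on incomplete forms, up to rounding of the mean. Each such form holds one to three, so K lies between Y/3 and Y. No shell counts K directly, and none separates incomplete forms from forms never returned. SAP 9.7 has no item-level table to accompany Table 62.

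**The case against.** The strongest reply is that this is a complete-form rule with its assumption stated openly. If blanks are random, the SAP figure is unbiased. An incomplete form then shows a 'Yes' no more often than a complete one, so in expectation the figure stays within the limits. The analysis is purely descriptive (SAP 8.1.1), without tests or decision rules (SAP 4.1 and 4.2), and this is one indicator of one secondary end point. All of that stands, and it fixes the weight of the point. It does not restore the discarded forms, and no other passage does.

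Four stronger readings are tempting, and the documents do not support them:

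- **The reported proportion is biased upwards.** This needs patients who skip items to be less adherent. No passage says so.
- **The excess has a known size.** The 1.25 to 3.75 points in the rows with half of the incomplete forms holding a 'Yes' depend on 75% adherence among complete forms. At 50% the excess is nil.
- **The tables hide the problem.** Tables 39 and 40 allow the indirect check in step 6. What they lack is a direct count.
- **Incomplete forms should simply be reclassified, including 'Poor' from three 'Yes'.** For the binary indicator alone this biases downwards under random blanks. For the three levels, one 'Yes', two 'No' and a blank is certainly 'Average', so restoring only 'Poor' forms would distort the distribution.

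**Conclusion.** The point holds in a limited form. The blank-item rule removes from the binary indicator forms whose class the SAP's own cut has already settled, and all of them are non-adherent. The reported proportion exceeds what the returned forms allow exactly when K/(K+U) > 1 − A/C. Whether that happens, and by how much, cannot be known from the documents: the illustrations run from no excess to 15 points, the latter with 20 of 100 forms incomplete and every one of those holding a 'Yes'.

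The rule remains sensible for the mean score and the three levels. The limits describe returned forms only. They say nothing about forms never returned, so they do not bound the proportion in the whole safety population. This is a minor improvement to a descriptive secondary indicator.

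**What to change.** In SAP 8.2.5.3:

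- Keep the complete-form rule for the mean score and the three adherence levels, and keep the complete-form adherent proportion A/C.
- For the binary indicator, class any form with a 'Yes' as non-adherent, four 'No' as adherent, and no 'Yes' with a blank as undetermined.
- Show K and U in Tables 40, 42 and 62. Beside A/C print the limits A/(C+K+U) and (A+U)/(C+K+U), labelled as applying to returned forms only (completed calls in Table 42).
- Add a footnote saying why the base of the limits differs from that of the 'High: 0' row, which stays on complete forms.
- Add no separate rule for 'Poor'.

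The cost is a few lines of SAP text and code. The downside is two extra values in a descriptive table. No new data are needed.

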8. STATISTICAL METHODOLOGY AND STATISTICAL ANALYSES

The statistical analyses will be performed on SAS software (version 9.4 or subsequent, SAS Institute, North Carolina USA).

8.1. *Statistical methods*

8.1.1. **Descriptive analyses**

The analysis will be purely descriptive.

The descriptive analysis of qualitative variables will include numbers and frequency of each modality. The analysis of quantitative variables will include mean, standard deviation, values, median and extreme values. The number of missing values or values analyzed will be shown for each variable studied.

Consistency between two qualitative variables (assessment of adherence at W4 and W6 of cycles 1, 2 and 4) will be assessed using the Kappa coefficient [3] (cf. interpretation of the Kappa coefficient in annex 11.1).

8.1.2. **Analysis strategy**

In the principal analysis of the primary objective, all patients included in the “Call Center” arm will be analyzed in this group regardless of the number of calls received and all of their data will be used.

The analysis will be performed on an overall basis and according to the number of calls made by the call center as defined in section §5. Analysis population.

The statistical analyses and tabular models stipulated in this SAP will be used subject to sufficient numbers being available for the expanded analysis for a given variable.

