Occasionally stops taking treatment when he/she feels better	Yes	xx (xx%)	xx (xx%)	xx (xx%)
	No	xx (xx%)	xx (xx%)	xx (xx%)
Occasionally stops taking treatment when he/she feels less well	Yes	xx (xx%)	xx (xx%)	xx (xx%)
	No	xx (xx%)	xx (xx%)	xx (xx%)
Additional question about the AE				
Occasionally reduced or adjusts treatment when an adverse event develops	Yes	xx (xx%)	xx (xx%)	xx (xx%)
	No	xx (xx%)	xx (xx%)	xx (xx%)

Table 42: Assessment of adherence in week 4 of cycles 1, 2 and 4 (safety population)

Carried out by telephone		Call, W4 cycle 1 (N=xxx)	Call, W4 cycle 2 (N=xxx)	Call, W4 cycle 4 (N=xxx)
MMAS-4 score (adherence score)*	Number analyzed	xxx	xxx	xxx
	Mean (\pm SD)	xx (\pm xx)	xx (\pm xx)	xx (\pm xx)
	Median	xx	xx	xx
	Min-Max	xx - xx	xx - xx	xx - xx
Level of adherence	High: 0	xx (xx%)	xx (xx%)	xx (xx%)
	Moderate: 1 or 2	xx (xx%)	xx (xx%)	xx (xx%)
	Low: 3 or 4	xx (xx%)	xx (xx%)	xx (xx%)
	Missing value	xx -	xx -	xx -
“Adherent” patient	Yes: 0	xx (xx%)	xx (xx%)	xx (xx%)
	No: ≥ 1	xx (xx%)	xx (xx%)	xx (xx%)
	Missing value	xx -	xx -	xx -

From 0 to 4: a low score represents improved adherence.

Table 43: Consistency between assessment of adherence at W4 (telephone) and W6 (self-completed questionnaire) in each cycle 1, 2 and 4 (safety population)

		Level of adherence at W6 (MMAS-4) Self-completed paper questionnaire			Coefficient Kappa
		High: 0 (N=xxx)	Moderate: 1 or 2 (N=xxx)	Low: 3 or 4 (N=xxx)	
Cycle 1	Level of adherence at W4 (MMAS-4) (telephone)	High: 0	xx (xx%)	xx (xx%)	xx (xx%)
		Moderate: 1 or 2	xx (xx%)	xx (xx%)	xx (xx%)
		Low: 3 or 4	xx (xx%)	xx (xx%)	xx (xx%)
		Missing value	xx -	xx -	xx -
		Level of adherence at W6 (MMAS-4) Self-completed paper questionnaire			Coefficient Kappa
Cycle 2		High: 0 (N=xxx)	Moderate: 1 or 2 (N=xxx)	Low: 3 or 4 (N=xxx)	
Level of adherence at W4 (MMAS-4) (telephone)	High: 0	xx (xx%)	xx (xx%)	xx (xx%)	xx
	Moderate: 1 or 2	xx (xx%)	xx (xx%)	xx (xx%)	
	Low: 3 or 4	xx (xx%)	xx (xx%)	xx (xx%)	
	Missing value	xx -	xx -	xx -	
		Level of adherence at W6 (MMAS-4) Self-completed paper questionnaire			Coefficient Kappa
Cycle 4		High: 0 (N=xxx)	Moderate: 1 or 2 (N=xxx)	Low: 3 or 4 (N=xxx)	
Level of adherence at W4 (MMAS-4) (telephone)	High: 0	xx (xx%)	xx (xx%)	xx (xx%)	xx
	Moderate: 1 or 2	xx (xx%)	xx (xx%)	xx (xx%)	
	Low: 3 or 4	xx (xx%)	xx (xx%)	xx (xx%)	
	Missing value	xx -	xx -	xx -	

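### SAP 8.2.5.3 and Table 43 measure agreement on an ordered three-level adherence scale with a kappa that has no stated weights, so High-Low and adjacent disagreements are not told apart

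*SAP*

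**What the plan says.** SAP 8.2.5.3 groups the MMAS-4 score into three levels that have a natural order:

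- "High adherence: score of 0"
- "Average adherence: score of 1 or 2"
- "Poor adherence: score of 3 or 4"

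Table 43 uses the same cut-offs and calls the second and third levels Moderate and Low; those labels are used below. Its title is "Consistency between assessment of adherence at W4 (telephone) and W6 (self-completed questionnaire) in each cycle 1, 2 and 4". It has a 3 x 3 layout with a single kappa cell for each of the three cycles.

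SAP 8.1.1 introduces the method as one for "Consistency between two qualitative variables". SAP 8.2.5.3 first acknowledges that the 0-4 score is a discrete quantity, then says that it "can be considered to be qualitative index", and concludes that the week 4 and week 6 consistency "will be considered using the Kappa coefficient". Annex 11.1 supplies fixed bands for reading the result, including 0.80-0.61 and 0.60-0.41.

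None of these places gives a weighting scheme. None of them uses the word unweighted either.

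**The concern.** Simple kappa gives credit only to exact matches and treats every other cell as an equal failure. That suits nominal categories. Here the levels are ordered, and the reason for the comparison makes the order matter. SAP 8.2.5.3 notes that answers given to a third party may carry a declaration bias. A patient who is High on the telephone and Low on paper is much stronger evidence of such a bias than one who moves between High and Moderate, which can come from one item answered differently.

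What is at stake is the summary figure for each cycle and the annex band in which it falls. Two tables with very different patterns of disagreement can produce the same kappa and the same band.

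**Working it through.** The documents state no kappa, expected agreement or cell count, so there is no figure of the plan's own to reproduce. The check asks how far the missing weights could matter.

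**Inputs**

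- Three ordered levels: SAP 8.2.5.3 and Table 43.
- Bands: SAP annex 11.1.
- n = 100: planned recruitment in SAP 2.2, used only as a convenient table size.
- Cell counts and margins: assumed. Both assessments are given margins of 60/30/10 (High/Moderate/Low); a sparse case of about 84/15/1 follows.

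**Formula**

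Kappa = (Po - Pe)/(1 - Pe), where Po and Pe are the observed and chance-expected agreement, each summed with agreement weights. Simple kappa uses 1 on the diagonal and 0 elsewhere. Linear weights are 1 on the diagonal, 0.5 for adjacent levels and 0 for High-Low. Quadratic weights are 1, 0.75 and 0.

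**Chance agreement with margins 60/30/10**

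- Simple: 0.36 + 0.09 + 0.01 = 0.46.
- Expected share in adjacent cells: 2(0.6 x 0.3) + 2(0.3 x 0.1) = 0.42.
- Linear: 0.46 + 0.5 x 0.42 = 0.67.
- Quadratic: 0.46 + 0.75 x 0.42 = 0.775.

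**Same margins, same raw agreement, different pattern**

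Table P is [[53,0,7],[0,30,0],[7,0,3]], with all 14 disagreements High-Low. Table Q is [[53,7,0],[7,23,0],[0,0,10]], with all 14 High-Moderate. Both have 86 of 100 on the diagonal.

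- Simple, P and Q: (0.86 - 0.46)/0.54 = 0.741.
- Linear, P: (0.86 - 0.67)/0.33 = 0.576.
- Linear, Q: (0.86 + 0.5 x 0.14 - 0.67)/0.33 = 0.788.
- Quadratic, P: (0.86 - 0.775)/0.225 = 0.378.
- Quadratic, Q: (0.86 + 0.75 x 0.14 - 0.775)/0.225 = 0.844.

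Simple kappa puts both tables in the 0.80-0.61 band. With linear weights Q stays there and P falls to 0.60-0.41.

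**A pair in which the order reverses**

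Table X is [[52,0,8],[0,30,0],[8,0,2]] and table Y is [[50,10,0],[10,18,2],[0,2,8]], with the same margins.

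- Simple: X (0.84 - 0.46)/0.54 = 0.704; Y (0.76 - 0.46)/0.54 = 0.556.
- Linear: X (0.84 - 0.67)/0.33 = 0.515; Y (0.76 + 0.5 x 0.24 - 0.67)/0.33 = 0.636.

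**Low level almost empty**

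- [[75,8,1],[8,6,1],[1,0,0]]: simple (0.81 - 0.7268)/0.2732 = 0.305; linear (0.895 - 0.8508)/0.1492 = 0.296.
- [[75,9,0],[9,6,0],[0,0,1]]: simple (0.82 - 0.7282)/0.2718 = 0.338; linear (0.91 - 0.8557)/0.1443 = 0.376.

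In both sparse tables, simple and linear kappa fall in the same band (0.40-0.21).

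**The case against.** The strongest case on the other side has four parts.

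1. *Exact agreement is a legitimate target.* Simple kappa answers how often the two answers match beyond chance. This stands, and it is the reason to keep simple kappa rather than replace it.

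2. *Weights bring their own arbitrariness.* Table P moves from 0.576 with linear weights to 0.378 with quadratic, which is another band. This also stands. It argues for naming the weights in advance, not for leaving them open.

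3. *The plan never says unweighted.* True. SAP 8.1.1 knows only qualitative and quantitative variables, so qualitative need not mean nominal there. Yet Protocol 8.7.2 names qualitative and ordinal variables separately, and a kappa without weights, justified by treating the score as qualitative, reads most naturally as the simple form. If a weighted form was meant, the same edit is needed.

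4. *Little depends on it.* SAP 8.2.5.3 and Protocol 7.3.2 present the comparison as informative only, because the questionnaire was not validated for use by an interviewer. The SAP makes it conditional on sufficient numbers, and SAP section 4 sets no tests and no decision rules. The adherence endpoints themselves, the mean score and the proportion adherent, do not use kappa. Table 43 shows every cell, so High-Low conflicts remain visible. All of this stands.

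A reader might go further and infer that the planned statistic will rank agreement the wrong way, or that the reported category will be wrong. The documents do not support that. No ranking of kappas across cycles is planned, and the counts above are assumed. In the reversing pair, X also has more exact agreement than Y (84% against 76%), so simple kappa is right on its own question when it places X higher.

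**Conclusion.** The point holds as one of low importance. On the plain reading, the planned kappa ignores the order of the three levels and cannot distinguish High-Low from adjacent disagreement. In the illustration this hides a difference of 0.788 - 0.576 = 0.212 on the linear-weighted scale, enough to cross an annex 11.1 band. That size depends on assumed margins in which a tenth of patients are Low. In the two sparse tables the change from simple to linear is 0.009 and 0.038. How many patients will score 3 or 4 is not stated, so the documents do not settle which case applies.

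A second, purely textual gap is certain: SAP 8.2.5.3 speaks of the 0-4 score when it introduces kappa, whereas Table 43 computes it on three levels. The two will in general give different values, and the SAP should say which one is meant.

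**What to change.** In SAP 8.1.1, SAP 8.2.5.3 and Table 43:

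- Specify linear-weighted kappa with a 95% CI, computed on the three levels of Table 43, and write out the weights (1, 0.5, 0).
- Keep simple kappa and add the raw percentage agreement beside it, for each of cycles 1, 2 and 4.
- Reword SAP 8.2.5.3 so that the variable entering kappa matches Table 43.
- State in annex 11.1 which of the two kappas the bands are applied to.

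This needs no new data and one option in the SAS call. The price is an additional reported figure and a choice of weights that is a convention. It should be settled before the cross-tabulations are seen, since weights chosen afterwards would be post hoc.
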